For the past two decades, adoption of a similar strategy of ventilation in the intensive care unit for patients with acute respiratory distress syndrome have yielded decreased mortality (8-10). However, uptake of LPV usage in the operating room has been slower, with less than 50% compliance (11, 12). Factors that influence compliance in some centers include extremes of patient IBW, unoptimized default ventilator settings, and clinician misconceptions surrounding LPV guidelines (12-14). While adherence to LPV was higher for COVID positive patients during the start of the COVID pandemic with evidence for lower mortality in the intensive care unit (15, 16), it is unknown whether an increase in overall LPV compliance occurred outside of COVID positive patients, and if so, whether such a shift in practice was sustained. In addition, most studies querying LPV compliance occurred in centers outside of Canada (12-14), with differences in medical education and practice patterns compared to Canadian centers. To fill these gaps in the literature, we therefore aim to explore patterns of LPV compliance in a large Canadian health authority in a retrospective manner, and to elucidate predictors influencing LPV compliance. We will also explore trends of LPV compliance throughout the COVID pandemic, into the post-pandemic era.

2. Purpose and Justification

The purpose of this study is to investigate patterns of LPV compliance, elucidate predictors of LPV compliance, and gauge the effects of COVID on LPV compliance in Fraser Health Authority. Although the use of nonprotective ventilation has decreased over time, a large proportion of patients continue to be ventilated with high tidal volumes and little PEEP(13, 17, 18). While the use of LPV strategies has been improved, patients that are short-stature, obese, or female have an increased tendency to be ventilated with larger tidal volumes in non-Canadian studies (11, 19). Contributing to this shortfall may be lack of patient height documentation as well as lack of awareness by providers regarding the significant impact of height (rather than patient weight) in determining LPV ventilation parameters. Compliance with LPV has been shown to be increased following implementing education about LPV, feedback regarding developmental performance, departmental LPV policies, and modification of default ventilator

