settings (12, 14, 19). Therefore, identifying patterns and predictors of LPV compliance in a Canadian context through our study may help inform the design of educational efforts and systemic changes to tackle areas of deficiency.

3. Research question

Primary research question: In patients undergoing general anesthesia with an endotracheal tube for non-cardiac surgery, what is the compliance rate to LPV in Fraser Health Authority, and predictors of such compliance?

Secondary research questions: What are time trends and shifts in LPV compliance from the pre-COVID to the post-COVID era? Are these trends sustained into the “new normal” era?

4. Research objectives and hypothesis

The objectives for this study are to:

1. Identify rates of compliance with LPV guidelines in the Fraser Health Authority in the Province of British Columbia, Canada. Compliance with ventilation guidelines is defined as meeting two criteria. The first is that their average tidal volume is 6-8 mL/kg IBW and the second is that the average positive end expiratory pressure (PEEP) is at least 5 cm H₂O. Patients ventilated according to one or neither of the above criteria will not be considered to have been ventilated according to the guidelines.
2. To elucidate predictors of compliance with LPV practice among providers. These predictors may help inform the design of educational efforts and systemic changes to tackle areas of deficiency.
3. To elucidate time trends and shifts in LPV compliance from the pre-COVID pandemic to post-pandemic era.
4. To evaluate whether time trends and shifts in LPV compliance through the pandemic are sustained.

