The primary hypothesis is that not all patients will be ventilated according to the recommended LPV strategy. We further hypothesize that patient height will be a major predictor in determining compliance to LPV, as our clinical experience suggests that while IBW used to set tidal volumes is calculated based on height, many anesthesiologists set tidal volumes by actual weight rather than IBW. Therefore, this practice may result in tidal volumes outside of a patient's acceptable tidal volume as would be recommended by LPV guidelines. Our other hypothesized predictors to LPV compliance include predictors that indicate respiratory dysfunction (e.g. severe COPD, CHF) or severe illness (American Society of Anesthesiologists [ASA] classification, sepsis), as anesthesiologists may be more cognizant of the need for LPV in these patients. Lastly, we hypothesize that the COVID pandemic will introduce a shift towards increased LPV compliance, but this shift may not be sustained in the post-pandemic era as precautions waned.

5. Methods

Study design

Our study is a retrospective cohort study investigating the correlation between hypothesized predictors of LPV compliance and actual LPV practice in a large multi-center health authority. The study population is all patients who underwent a general anesthetic for any procedure at a Fraser Health Authority hospital from January 2014 – December 2023. See Section 7 for more details regarding inclusion and exclusion criteria.

Sampling and sample description

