We aim to use convenience sampling by including all patients who meet eligibility criteria. All procedures conducted under general anesthesia within the Fraser Health Authority with an endotracheal tube for over 30 minutes and within the date range specified that meet the inclusion criteria are eligible for inclusion in this study. This is a multicentre study and includes all hospitals within the Fraser Health Authority using Centricity Perioperative Anesthesia (CPA) system, which collects intraoperative data. The American College of Surgeons National Surgical Quality Improvement Program (NSQIP) is an outcomes-based program to measure and improve the quality of surgical care by tracking patient data preoperatively through 30-days postoperatively; NSQIP data will be used for perioperative variables such as comorbidities. Procedures must be followed by NSQIP and currently within the CPA database to be included in our study (see inclusion and exclusion criteria). Based on historical data and the surgical volume contributing to the Fraser Health CPA system we expect there to be approximately 100,000 cases.

Inclusion and exclusion criteria

Inclusion criteria for this retrospective study include any patient that is over the age of 18 and underwent general anesthesia with endotracheal tube placement for a procedure lasting ≥ 30 minutes. Patients must be included in the NSQIP database and linked to their anesthetic dataset within CPA by either their name, date of birth, medical record number (MRN, i.e. RC number), Personal Health Number (PHN), and/or date of surgery. Exclusion criteria for this retrospective study include: any patient that underwent cardiac or thoracic surgery or received an anesthetic that did not utilize an endotracheal tube, ASA 6 (organ donor), Hyperthermic intraperitoneal chemotherapy, transplant cases, surgical procedure related to an occurrence or complication of prior procedure during the same admission/within 30 days, multiple National Surgical Quality Improvement Program (NSQIP) assessed cases within 30 days only for same patient, cases in CPA that are unable to be linked to NSQIP data or vice versa.

6. Data collection

Data sources

Predictors and demographic data: The American College of Surgeons National Surgical Quality Improvement Program is a validated, risk adjusted, outcome-based program that measures the

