- Our list of hypothesized predictors to LPV use include:
 - Age
 - sex
 - height
 - obesity (body mass index > 30)
 - elective/emergency
 - ASA Class
 - sepsis
 - functional health status
 - anesthesia duration
 - dyspnea
 - severe COPD
 - CHF
 - smoker
 - surgical specialty
 - ventilatory dependent
 - Pre-COVID era vs. COVID era
 - Night or weekend shift (1)
 - Hospital site
 - Use of neuromuscular blockade
 - Presence of epidural anesthesia
 - Inpatient vs. outpatients
 - Laparoscopic surgery
 - Transfusion of blood products
 - Dialysis
 - Ascites
 - NB: We considered before January 2020 as the pre-COVID era, and after June 2020 as the COVID era. The former cutoff was chosen as January 2020 contained the first COVID case in BC. The latter cutoff was chosen as it constitutes three months after March 2020, when the World Health Organization announced COVID's pandemic status, and BC announced a state of emergency with the start of isolation policies. We hypothesized that any impact of the COVID pandemic on LPV compliance patterns would unlikely to have occurred prior COVID's arrival in BC, but would likely be in full swing three months after initiation of widespread social isolation, a very palpable event in society.
 - NB2: parameters such as oxygen saturation, end-tidal carbon dioxide, and peak inspiratory pressures may be affected by use of LPV, and therefore will not be included as candidate predictors due to high likelihood of reverse causation (2). Mode of ventilation has been shown to correlate with LPV compliance(2), but this is unfortunately not recorded in our dataset.
- To screen for inclusion in the multivariate logistic regression model, the association of each hypothesized predictor to LPV use will be first explored using bivariate analyses.

Chi squared test will be used for categorical hypothesized predictors (or Fisher's exact test if a covariate pattern results in < 5 cases). Bivariate logistic regression (including only the predictor and LPV) will be used for continuous hypothesized predictors.

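### Part III treats all months after June 2020 as one era, so Objective 4 (was the shift sustained?) gets chart signals but no case-mix-adjusted estimate

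*Combined protocol and SAP*

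**What the plan says.** Section 3 asks "What are time trends and shifts in LPV compliance from the pre-COVID to the post-COVID era", and then whether the trends persist into a new-normal period. In Section 4, Objective 3 is "To elucidate time trends and shifts in LPV compliance from the pre-COVID pandemic to post-pandemic era" and Objective 4 is "To evaluate whether time trends and shifts in LPV compliance through the pandemic are sustained". The hypothesis is that compliance rises with COVID but that "this shift may not be sustained in the post-pandemic era as precautions waned". Section 2 gives as one purpose to "gauge the effects of COVID on LPV compliance in Fraser Health Authority".

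Section 7 handles time in two places.

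- **Part II** is a monthly p chart of compliance with eight run rules. Subgroup charts are planned for academic sites, laparoscopic surgery, and patients whom the default tidal volume would leave outside the criteria.
- **Part III** is a logistic model in which era is kept whatever the screening result. Era is defined in the first NB: "We considered before January 2020 as the pre-COVID era, and after June 2020 as the COVID era". Neither the predictor list nor the forced-in terms include year, month or any other calendar-time variable.

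One Part III sensitivity analysis resets the era cut-offs to dates signalled by the chart. It still describes the contrast as pre-COVID versus COVID, names no third level, and does not say how several signalled shifts would be coded.

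**The concern.** The hypothesis predicts a rise and then a fall. An odds ratio that averages the pandemic and post-pandemic months cannot support or refute it. A reader who wants to know how much of the shift remained, after allowing for changes in patients, sites and procedures over ten years, will find no estimate and no interval.

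There is a second, conditional problem. With no calendar-time term, the era odds ratio compares months that lie on average more than five years apart. Section 2 says of the literature that "Although the use of nonprotective ventilation has decreased over time". If compliance was already rising locally before 2020, part of the era odds ratio is that rise, yet it could be reported as a COVID effect.

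**Working it through.** The plan gives no effect size, baseline compliance or precision for the era contrast, so there is no figure to reproduce.

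**Inputs from the documents.** The window is January 2014 to December 2023, or 120 months. On volume, "we expect there to be approximately 100,000 cases" (Section 5), so 100,000 / 120 = 833 a month. The era dates give 72 pre-COVID months, 42 later months, and 6 months (January to June 2020) in neither era.

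**Assumptions, not in the documents.** Baseline compliance 30%, equal monthly volume, and a post-pandemic split at July 2022 (24 pandemic and 18 post-pandemic months). No case-mix covariates are simulated.

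**1. Reverted or lasting?** The two-level odds ratio depends only on average compliance in each era.

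- A 10-point rise lost after 24 months: (24 × 0.40 + 18 × 0.30) / 42 = 0.357.
- A lasting rise of 10 × 24/42 = 5.7 points: 0.357.
- Either way, (0.357/0.643) / (0.300/0.700) = 1.30.

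| Pattern (30% baseline) | Two-level OR | Pandemic vs pre | Post-pandemic vs pre | Post-pandemic vs pandemic |
|---|---|---|---|---|
| +10 points, then lost | 1.30 | 1.56 | 1.00 | 0.64 |
| +5.7 points, lasting | 1.30 | 1.30 | 1.30 | 1.00 |
| +10 points, half lost | 1.42 | 1.56 | 1.26 | 0.81 |

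The first two patterns also coincide at a 15% baseline (both 1.48) and at 50% (both 1.26). With a 40% baseline and a 21/21-month split, a lasting 5-point rise and a 10-point rise that reverts both give 1.23.

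**2. Trend with no COVID effect.** For an annual trend odds ratio r, the era odds ratio is close to r raised to the distance in years between the era midpoints. The pooled eras are 63 months apart, or 5.25 years: 1.03^5.25 = 1.17 and 1.05^5.25 = 1.29. Fitting the logistic model to expected counts gives 1.11, 1.17, 1.29 and 1.64 for r = 1.02, 1.03, 1.05 and 1.10, and 1.00 for r = 1.

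Three levels do not remove a trend. At r = 1.05, post-pandemic versus pandemic (21 months apart) reads 1.09, and post-pandemic versus pre-COVID (75 months apart) reads 1.35.

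**3. What the chart can do.** The plan does not state the centre line. Take the mean of all 120 months, with January to June 2020 at baseline: 0.32. Sigma is √(0.32 × 0.68 / 833) = 0.0162. The reverting pattern sits at (0.40 − 0.32)/0.0162 = +4.9 sigma and then −1.2. The lasting pattern sits at +2.3 throughout. The run rules would separate them.

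**4. Half-year odds ratios against 2019.**

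- A gradual return from July 2021 to July 2023 reads 1.56, 1.56, 1.49, 1.34, 1.20, 1.07, 1.00 from the second half of 2020 onward.
- A continuing trend of 1.05 a year with no COVID effect reads 0.77 in the first half of 2014 and 1.23 in the second half of 2023. The trend is not removed, but it can be seen.

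**5. Precision.** The SE of a log odds ratio is √[1/(n₁ × 0.21) + 1/(n₂ × 0.21)], where 0.21 = 0.3 × 0.7.

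- Post-pandemic vs pre-COVID (14,994 and 59,976 cases): 0.020.
- Post-pandemic vs pandemic (14,994 and 19,992): 0.024.
- One half-year vs 2019 (4,998 and 9,996): 0.038, or about ±8%.

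These ignore clustering. An assumed extra month-to-month SD of 0.05, 0.10 or 0.15 on the log-odds scale multiplies them by 1.20, 1.66 or 2.22.

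**The case against.** The strongest reply is that Section 7 gives time trends to Part II and predictors to Part III. The era term serves Objective 2, and nowhere does the plan say its odds ratio will settle whether the shift lasted. The chart does that, and step 3 shows it would separate the two patterns. A chart over all 120 months would also display a pre-2020 trend. This stands. A reader might infer that Objective 4 has no analysis at all, and the documents do not support that. What remains is narrower: the chart is unadjusted and yields no size or interval. Nothing in the documents shows that case mix changed enough to mislead the chart, and nothing shows that it did not.

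The sensitivity analysis speaks of dates in the plural, so it could perhaps be read as allowing an end to the COVID era. It does not exclude a third level. But it names none, and its dates would come from the same outcome data.

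The trend argument is conditional. A reader might infer that the era odds ratio is biased by a secular rise. The documents report no local trend, only the direction of one in the literature. Sections 5 and 7 mostly use the language of correlation, although Section 2 speaks of effects.

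**Conclusion.** The point holds in this limited form. Objectives 3 and 4 have a descriptive analysis that can show a reversal. The only adjusted era estimate cannot, because 42 months are pooled and the post-pandemic era has no date. That the two patterns share one odds ratio is exact arithmetic; its size (1.30) rests on the assumed 30% baseline, equal monthly volume and July 2022 split. The trend component ranges from none to an odds ratio of 1.64 across annual trends of 1.00 to 1.10, and the documents do not say where in that range the health authority lies.

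It should be fixed before analysis. It concerns secondary objectives and one predictor. A reader should not extend it to the overall compliance rate, which does not depend on the era coding.

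**What to change.** 1. State a post-pandemic start date before the chart is viewed, and use three era levels in Part III. Report post-pandemic versus pandemic and post-pandemic versus pre-COVID odds ratios, with intervals, beside the chart.
2. From the same covariate model, with half-year indicators in place of era, report odds ratios against 2019. These need no split date and show both an earlier trend and a reversal.
3. If the pre-2020 half-year odds ratios show a trend, describe the era odds ratio as a before/after association, not a COVID effect.

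I would not add a spline in calendar time to the three-level model. With no secular trend and full reversion six months before the chosen split, a 4-knot spline gives 1.58 for post-pandemic versus pre-COVID where the truth is 1.00. It gives 1.83 for pandemic versus pre-COVID, against 1.40 from three levels alone. For the same reason, a difference between fits with and without a trend term should not by itself decide the wording, since a mis-dated split would then downgrade a real shift.

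Minor: keep year and month of surgery in the analysis file. Section 9 (A.14) deletes date of surgery after linkage, while Section 6 extracts it for the chart and era status and A.5 lists it as needed for collection and/or analysis. These sections must be reconciled.

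The cost is some SAP wording and a few model terms, using dates already to be extracted, and the lower precision shown in step 5.

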- We will use a multivariate logistic regression model to determine the independent predictors of LPV use. Predictors with a $p < 0.2$ in the bivariate analysis will be incorporated into model construction. A conservatively high cut-off for the p-value was chosen to minimize type II error (exclusion of a predictor that would have become significant if adjusted for other predictors in the multivariate model). For the same reason, we will not adjust the p-value for multiple comparisons during the predictor screening phase.
- For face validity, we will include age, sex, height, obesity status, night or weekend shift, hospital site, laparoscopic surgery, and pre-COVID era vs. COVID era in the model regardless of bivariate analysis results.
- We will add candidate predictors that passed the bivariate phase in a forward selection method, minimizing the Akaike Information Criterion (3), which rewards improved goodness of fit while simultaneously penalizes over-fitting.
- Pairwise interaction among included terms will be investigated via adding an interaction term for each pair, and comparing the model with and without the interaction term via a likelihood ratio test. A $p < 0.05$ will result in inclusion of that interaction term. As before, to minimize type II error, the p value will not be adjusted for multiple comparison at this stage.
- Finally, the odds ratio of each predictor for LPV use in the final model will be presented with and without Bon Ferroni adjustment for multiple comparisons. A separate result will be presented for interactions, if any are detected.

Sensitivity analyses, subgroup analyses, and other supplemental analyses

- Part I: none planned
- Part II:
 - Subgroup analysis for: academic hospital sites, laparoscopic surgery.
 - Subgroup analysis for patients who would not have met LPV criteria if ventilated by default ventilator settings for tidal volume. This analysis explores whether clinicians became more likely to adjust the ventilator settings intentionally to achieve LPV.
- Part III:
 - We will adjust the date cut-offs for pre-COVID era vs. COVID era based on Shewhart chart results of Part II (i.e. the dates that the Shewhart chart indicated shifts in practice pattern)
 - Subgroup analysis for academic hospital sites only.

8. Ethical considerations

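### Part III can drop or exaggerate rare, weak or masked predictors among the 17 left to screening and forward AIC, although the expected sample supports fitting all 25

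*Combined protocol and SAP*

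**What the plan says.** Section 7, Part III opens its list with "Our list of hypothesized predictors to LPV use include" and gives 25 items. Model building then runs as follows.

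- Eight items enter whatever the bivariate results: "we will include age, sex, height, obesity status, night or weekend shift, hospital site, laparoscopic surgery, and pre-COVID era vs. COVID era".
- The remaining 17 face a crude test: "Predictors with a $p < 0.2$ in the bivariate analysis will be incorporated into model construction". The reason given is that "A conservatively high cut-off for the p-value was chosen to minimize type II error", meaning the loss of a predictor that would matter once adjusted.
- A second filter follows: "We will add candidate predictors that passed the bivariate phase in a forward selection method, minimizing the Akaike Information Criterion".
- All pairs of included terms are tested for interaction at p < 0.05, unadjusted, and those that pass are added.
- Odds ratios are shown for predictors in the final model, "with and without Bon Ferroni adjustment for multiple comparisons".

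Section 4 puts height first among the hypotheses. It continues: "Our other hypothesized predictors to LPV compliance include predictors that indicate respiratory dysfunction (e.g. severe COPD, CHF) or severe illness", with ASA class and sepsis as the illness examples, and closes with a COVID-era shift. Section 5 says of the sample that "we expect there to be approximately 100,000 cases". No full-model analysis, shrinkage, bootstrap or other correction for selection is planned.

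**The concern.** Predictors of compliance are half of the primary research question in Section 3. A predictor that fails either filter gets no adjusted OR and no interval, so a reader cannot tell an absent effect from an imprecise one. This can happen to severe COPD, CHF, ASA class and sepsis, because none of them is forced in. A rare or weak predictor that survives does so partly because its estimate happened to be large. Its OR is then too far from 1 on average, while the interval and the Bonferroni correction treat the surviving set as if it had been chosen beforehand.

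The screen is also a doubtful means to its stated end. A crude p-value cannot show whether a predictor will matter after adjustment. If other variables mask it, a lenient cut-off may still remove it.

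**Working it through.** The plan has no power or events-per-parameter calculation to reproduce. From the documents: 25 predictors, 8 forced, 25 − 8 = 17 selected; N about 100,000; screen at p < 0.2. Assumed, because the documents give no values for this cohort: predictor prevalence, true OR and compliance (30% unless stated).

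**1. Is selection needed?** Events per parameter = N × compliance / df.

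- 10% compliance, 25 df: 100,000 × 0.10 / 25 = 400.
- 10% compliance, 100 df (a generous allowance for multi-level specialty, site and ASA): 10,000 / 100 = 100.
- 50% compliance, 25 df: 50,000 / 25 = 2,000.
- Only 20,000 linked cases, 10% compliance, 60 df: 2,000 / 60 = 33.

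A full main-effects model is comfortably supported.

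**2. Retention and exaggeration.** For a binary predictor of prevalence π, SE(log OR) ≈ 1/√(N × π × 0.3 × 0.7), and d = log OR / SE. The screen keeps |z| > 1.282. AIC with 1 df keeps |z| > √2 = 1.414, so without confounding AIC is the stricter filter.

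- P(kept) = Φ(d − 1.414) + Φ(−d − 1.414).
- Mean z when kept = d + [φ(1.414 − d) − φ(1.414 + d)] / P(kept).

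Example at π = 0.5%, OR 1.2:

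- SE = 1/√105 = 0.0976; d = 0.1823 / 0.0976 = 1.868.
- P(kept) = Φ(0.454) + Φ(−3.282) = 0.676.
- Mean z when kept = 1.868 + (0.360 − 0.002) / 0.676 = 2.40.
- Mean log OR = 2.40 × 0.0976 = 0.234, so OR 1.26.

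| Prevalence | True OR | Kept by AIC | Mean OR when kept |
|---|---|---|---|
| 0.1% | 1.2 | 29% | 1.51 |
| 0.2% | 1.2 | 41% | 1.38 |
| 0.5% | 1.2 | 68% | 1.26 |
| 1% | 1.2 | 89% | 1.22 |
| 2% | 1.2 | 99% | 1.20 |
| 0.5% | 1.3 | 90% | 1.33 |
| 1% | 1.3 | 99% | 1.30 |
| 1% | 1.1 | 49% | 1.16 |

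Coverage of the 95% CI when kept, at OR 1.2, is 96%, 93% and 87% for 0.5%, 0.2% and 0.1% prevalence. At OR 1.1 and 0.1% prevalence it is about 75%.

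**3. Masking.** A simulation (2,000 replicates, N = 100,000) used a confounder present in half the cases with OR 0.5 for compliance. The predictor had 1.5% prevalence with the confounder and 0.5% without it, and an adjusted OR of 1.3. Its crude OR averaged 1.08. The p < 0.2 screen dropped it in 55% of replicates, although the full model had 96% power at 0.05. In 52% of replicates it was dropped and would have been significant in the full model. That is the error the cut-off was meant to avoid.

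**4. Interactions.** With 25 terms there are 25 × 24 / 2 = 300 pairs. At p < 0.05 about 300 × 0.05 = 15 would enter by chance under the null. With the eight forced terms alone there are 28 pairs, or about 1.4.

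**The case against.** The plan states its method in advance, explains its lenient cut-off and forces in key variables. A reader might infer that the main hypotheses are at risk, or that every surviving OR is biased. The documents support neither. Height and COVID era are forced in. At this sample size, a predictor of 2% prevalence or more with an OR of 1.2 or more is almost always kept and essentially unbiased by selection. A reader might also take ascites, dialysis and ventilator dependence for named hypotheses. They are on the Part III list, but Section 4 does not name them, and nothing says how rare they are.

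Two further objections stand. First, the full model gains little power in the worst cells: at 0.1% prevalence and OR 1.2, power is about 13% at 0.05 and about 1% after Bonferroni over 25, with a typical interval of 0.78 to 1.84. The gain is an honest wide interval. Second, listing every predictor is not enough by itself. The interaction search would still alter the reported model. Section 6 also describes sepsis by a postoperative window and lists transfusion both before surgery and during or after it. Part III excludes other variables for reverse causation, so these two need the same scrutiny.

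None of this gives a reason to keep the selection as the primary analysis.

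**Conclusion.** The concern holds within limits. Selection among the 17 unforced predictors can drop those that are very rare (roughly 0.5% or below), weak (OR near 1.1) or masked in crude analysis, and can exaggerate rare or weak ones that survive. It is not shown that any particular predictor will be dropped: that depends on prevalences, effect sizes and compliance that the documents do not give. Two parts do not depend on prevalence: four named hypotheses have no guaranteed adjusted estimate, and a crude screen cannot guarantee its stated purpose. Over-fitting is no counterweight at about 100,000 cases. The plan should change because the analysis serves the primary question and the remedy costs little, not because the results would otherwise be invalid.

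**What to change.** - Make one pre-specified main-effects model with all listed predictors the primary Part III analysis, without screening or forward selection.
- Before fixing the list, define sepsis and transfusion so that each precedes ventilation or cannot result from it, and state which data fields are used.
- Report every adjusted OR with its CI, and apply Bonferroni over that fixed list.
- Keep the bivariate results as a descriptive column and any AIC-selected model as secondary.
- Report the pairwise interaction search separately as exploratory, so that it does not change the primary ORs.

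No new data are needed and steps are removed. The cost is slightly wider intervals from unneeded terms, negligible at this size. Very rare predictors will have wide intervals.
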